7.3.3 Serious Adverse Events

Serious adverse events are those events that result in death, are life-threatening, require or prolong inpatient hospitalization, result in persistent or significant disability/incapacity, or cause congenital anomaly/birth defect.

All SAEs will be provided in listing and the incidence will be summarized in the overall summary of TEAE table.

7.3.4 Other Important Adverse Events

TEAEs leading to death and study drug discontinuation will be presented in separate listings and the incidence will be summarized in the overall summary of TEAE table.

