4.3 Patient Discontinuation/Withdrawal Criteria

Patients can withdraw from participation in this study at any time, for any reason, specified or unspecified, and without prejudice.

Patients must be withdrawn from study participation for the following reasons:

[figure not shown]
- It is determined by Day 1 pathology review that the patient has histology other than low-to intermediate-risk NMIBC
- Development of an adverse event (AE) that interferes with the patient's participation
- Patient withdrawal of informed consent
- Investigator decision
- Sponsor decision
- The patient refuses further follow-up study procedures, including cystoscopy
- The patient is lost to follow-up (missed at least two consecutive follow-up cystoscopies)
- Patient has a cystectomy
- Patient has a histologically-confirmed recurrence
- Death
- Pregnancy

The reason for the patient discontinuing study treatment or terminating from the study must be recorded on the case report form (CRF). For patients who discontinue from the study during the follow-up period or who are withdrawn, the date of last contact will be the final visit.

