7.3.1 Recording of Adverse Events

From the time the study Informed Consent is signed through the day of study drug administration, only SAEs that are related to study procedures are to be recorded. For all non-Target population patients, all adverse events from the time of study drug administration until Day 35 (± 5 days) post-TURBT will be recorded. For Target population patients, all adverse events will be recorded from the time of study drug administration until the 3-month Follow-up Visit. Only AEs related to study procedures and deaths will be recorded from the 3 month visit until a recurrence or the remainder of the follow-up period, whichever comes first.

All AEs should include resolution at the End-of-Study for a patient. The following conventions should be followed when patient completes or discontinues from the study

- If a patient dies, the date of death should be the date of AE stop for all ongoing AEs at the time of death.
- If a patient discontinues study drug due to an AE(s), the outcome of the AE is to be followed for 35 days (± 5 days) from the date of discontinuation or until the AE has returned to Grade ≤ 1 or returned to baseline conditions for the patient.

The status of the AE and the date of last contact with the patient will be captured. If the AE has not returned to Grade ≤ 1 or to Baseline conditions for the patient by the End-of-Study, the AE stop date should be left as ongoing.

All AEs will be classified by intensity/severity ([Section 7.3.2](#)), relationship to study drug ([Section 7.5](#)), and as serious or nonserious ([Section 7.7](#)).

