7.7.1 Serious Adverse Event Reporting

From the time the Informed Consent is signed until Day 1 of the study, only SAEs related to study procedures will be recorded. All SAEs that occur from the first dose of study drug administration until Day 35 (± 5 days) post-TURBT will be recorded. All SAEs related to study procedures will be recorded for the remainder of the follow-up period and are to be reported to Spectrum within 24 hours of knowledge of the event.

SAEs are to be reported and the serious adverse event report (SAER) faxed or emailed within 24 hours of knowledge of the event to:

Spectrum Pharmaceuticals, Inc.
Primary Contact: Pharmacovigilance Department
Fax: [REDACTED]
E-mail: [REDACTED]

Spectrum or its designee may request additional information from the Investigator to ensure the timely completion of accurate safety reports. Safety data that are critical to the reportability of an SAE, such as causality assessment and serious criteria, should be included in the initial faxed SAER. If omitted, a timely response to drug safety data queries received from Spectrum or a Spectrum designee is expected.

The Investigator is to take all appropriate therapeutic measures necessary for resolution of the SAE. Any medications necessary for treatment of the SAE are to be recorded in the concomitant medication section of the patient's CRF.

SAEs that are study-treatment related will be followed until resolution or until they have returned to Baseline/Grade 1, whichever is longer, or until it is determined that the outcome will not change with further follow-up.

Additionally, the SAE is to be entered in the AE section of the CRF. Follow-up SAERs need to be submitted to Spectrum within 24 hours, once additional information regarding the event becomes available (eg, diagnosis is made, laboratory or test results, event course, outcome, etc).

Spectrum/designee will be responsible for reporting SAEs to the regulatory authorities in accordance with applicable expedited reporting regulatory guidelines. The Investigator is responsible for submitting SAEs to his/her Institutional Review Board (IRB)/Ethics Committee (EC). Copies of each SAER, and documentation of IRB/EC notification and acknowledgement of receipt, will be kept in the Site's Regulatory Binder.

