8.6.1.2 Deaths

All deaths reported during the study will be tabulated and summarized by treatment arm.

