5 STUDY PATIENTS

5.1 Disposition of Patients

Patients in defined populations as shown in **Section 4.6** and reasons for discontinuation will be summarized by randomized treatment arms.

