7.3.1 Treatment Emergent Adverse Events

A TEAE is any AE that occurs from the first dose of study treatment until 35 days after the last dose of study drug administration. TEAEs will be graded according to National Cancer Institute

Common Terminology Criteria for Adverse Events (NCI CTCAE) version 4.03, and grouped by the MedDRA preferred term, and summarized by worst grade severity per patient by treatment arms.

The incidences of treatment emergent AEs will be presented by MedDRA SOC and PT with any grade and with Grade 3 or 4. Patients who experience more than one type of AE will be counted under each of the corresponding PT. Patients who experience different episodes of the same AE will be counted only once under the corresponding PT. Similarly, for determination of MedDRA SOC incidences, patients who experience multiple AEs under the same SOC will be counted only once for that SOC. Listing of all TEAEs will also be provided.

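### The safety-only SAP reduces laboratory results to a listing and names no table of all deaths by arm, although the protocol plans both by-arm summaries and the SAP declares neither change

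*SAP*

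**What the plan says.** **Status of the two endpoints.** SAP 2.1 leaves safety as the sole objective. SAP 3.4.2 lists routine hematology and chemistry, and deaths, among the safety endpoints. SAP 4.7 confines the final analysis to safety.

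**Laboratory data.** SAP 7.4 applies CTCAE grades where applicable and gives a listing as the only output. It describes sampling as pretreatment and continuing across the study. Protocol 8.6.3 names three collection points (Screening, Day 1 and the Safety Follow-up Visit) and plans a summary of worst grade per patient by treatment arm.

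**Deaths.** SAP 7.3.4 states: "TEAEs leading to death and study drug discontinuation will be presented in separate listings", with their incidence in the overall TEAE table. SAP 7.3.1 defines a TEAE as "any AE that occurs from the first dose of study treatment until 35 days after the last dose". Protocol 8.6.1.2 is wider: "All deaths reported during the study will be tabulated and summarized by treatment arm". Protocol 7.3.1 carries death recording past the window: "Only AEs related to study procedures and deaths will be recorded from the 3 month visit until a recurrence" or for the rest of follow-up, whichever is shorter.

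**Other places where a death could surface.**
- SAP 5.1: "reasons for discontinuation will be summarized by randomized treatment arms". Death is on the protocol 4.3 list introduced by "Patients must be withdrawn from study participation for the following reasons".
- SAP 7.3.3: "All SAEs will be provided in listing and the incidence will be summarized in the overall summary of TEAE table".

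**Declaration.** The SAP's Summary of Changes presents what it calls the important changes. Its five items cover efficacy objectives, efficacy endpoints, three analysis populations, the interim analysis, and sensitivity and subgroup analyses. None is a safety output. SAP section 1 says the SAP supersedes analysis procedures in other documents.

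**The concern.** Early termination explains why efficacy was removed. The SAP gives no reason for reducing the safety output as well, and safety is all that remains. Because the SAP supersedes the protocol's procedures, the two protocol summaries cannot be assumed to survive.

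The trial gives 8 mg in 50 mL, against 4 mg in 40 mL in the earlier Phase 3 trials. Protocol 1.3.2 reports an arm-level laboratory comparison for the earlier program and found no clinically meaningful difference from placebo. Under SAP 7.4 the same comparison at 8 mg would have to be assembled by the reader from a patient listing. For deaths, the safety tables by actual treatment would count fatal TEAEs but not necessarily all deaths. What is at stake is completeness of descriptive safety reporting; no error rate, power or efficacy claim is affected.

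**Working it through.** The plan states no figure on this point, so there is none to reproduce. The check is a comparison of sections, plus two small calculations.

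**1. Can the TEAE tables stand in for the laboratory summary?** Protocol 5.3.4 and footnote a of the schedule place the scheduled post-treatment CBC and chemistry of Target patients at Month 3, within 30 days either side. Taking Month 3 as day 91:
- earliest draw after the TEAE window closes: (91 − 30) − 35 = 26 days
- latest draw: (91 + 30) − 35 = 86 days

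An abnormality first seen at that draw would ordinarily be dated after the window and so would not count as a TEAE. Protocol 7.2 also makes a laboratory value an adverse event only under conditions such as clinical significance or an intervention, so many graded values would never reach those tables. Target patients were planned as 425/500 = 85% of enrollment; the actual proportion is not given.

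**2. Which outputs would show a death from an event starting after Day 35?**
- Fatal-TEAE row and listing (SAP 7.3.4): no, by definition.
- Disposition (SAP 5.1): yes, as a reason for discontinuation, by randomized arm.
- SAE listing (SAP 7.3.3): uncertain. Protocol 7.7.1 says "All SAEs related to study procedures will be recorded for the remainder of the follow-up period", and deaths are recorded alongside that. Whether a late death unrelated to procedures enters the SAE data is not stated.
- SAP 4.1 with SAP section 7: the general rule tabulates categorical variables by arm, and safety endpoints are evaluated by treatment received. This could support a count by actual arm but does not name one.

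**3. How many such deaths?** Inputs:
- about 3% of patients with fatal events over roughly two years (protocol 1.3.2)
- hazard rate of 0.3 for placebo recurrence and HR 0.65 (protocol 8.1). The unit is assumed to be per year. As a check, the earlier pooled placebo rate of 45.5% at two years gives −ln(0.545)/2 = 0.303.
- 85% Target patients, randomized 2:1, with death recording ending at recurrence
- follow-up of 6 or 12 months, and 0, 30 or 60 days from event onset to death (assumptions; SAP 3.3 says only that nobody exceeded 24 months)

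Death hazard: h = −ln(0.97)/730 = 0.0000417 per day. Recurrence exit: r = 0.3/365 for placebo and 0.3 × 0.65/365 = 0.195/365 for Qapzola. Recorded deaths per Target patient between days a and b:

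D(a, b) = h/(h + r) × [exp(−(h + r)a) − exp(−(h + r)b)]

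With lag L, a death falls outside the TEAE count if it occurs after day 35 + L. Example for L = 0 and 12 months:
- placebo: 0.0483 × (0.9702 − 0.7296) = 0.01162
- Qapzola: 0.0724 × (0.9800 − 0.8104) = 0.01229
- combined: 0.85 × (0.01162 + 2 × 0.01229)/3 = 0.0103, or 1.03 per 100 treated

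| Follow-up | L = 0 | L = 30 days | L = 60 days |
|---|---|---|---|
| 6 months | 0.48 | 0.38 | 0.28 |
| 12 months | 1.03 | 0.92 | 0.82 |

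These are later-onset deaths per 100 treated, both arms together. A two-year rate of 2% or 4% changes 1.03 to 0.68 or 1.37. Protocol 1.3.2 also reports no deaths within 30 days of instillation in the earlier trials. Moving the same 3% into the remaining 700 days multiplies the hazard by 730/700 = 1.043, so 0.28 becomes about 0.29 and 1.03 about 1.07.

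**The case against.** The strongest reply concerns deaths. The disposition table covers the Safety Population, death is a withdrawal reason, and a Target patient who dies before recurrence should be counted there by arm. Non-Target patients are followed only to about Day 35, where a fatal event should fall in the TEAE row. Randomized and actual arm differ only if a patient received the wrong kit, and protocol 8.2 makes kits patient-specific. SAP 4.1 with section 7 may also support a count by actual arm. All of this stands, and it is why deaths are the lesser point. What remains is that no section names the table the protocol promised.

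A reader might infer that most deaths would go unreported, since the TEAE window is short relative to follow-up. The documents do not support that. The share of deaths outside the TEAE row is not the share missing from all by-arm output, because disposition should count the later ones. Such a share would also depend heavily on the early hazard, so none is offered here.

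On declaration, the Summary of Changes claims to cover only important changes, protocol section 8 calls itself a brief overview, and protocol 8.4 leaves details to the SAP. The omission is therefore weak evidence of anything beyond incomplete drafting. It still leaves a reader unable to tell whether the reductions were intended.

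On laboratory data, one may say that a listing suffices for a terminated, descriptive report. That is a defensible preference if stated, but SAP 7.4 is specific and overrides the general by-arm rule, so no comparison would be produced. One limit applies: footnote a also sends patients who discontinue during follow-up to the Day 35 visit, so the Month 3 timing describes the scheduled draw and not every patient.

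**Conclusion.** The point holds as a minor reporting gap, and its laboratory half is the stronger. As written, the SAP produces no by-arm summary of a retained safety endpoint that protocol 8.6.3 would have summarized, and the TEAE tables cannot replace it for Target patients. For deaths, the gap is the absence of a named count of all deaths by actual arm.

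The expected number of later-onset deaths is roughly 0.3 to 1.0 per 100 treated, both arms together. That range rests on 6 to 12 months of follow-up, the earlier trials' death rate, the planned 85% Target proportion and death recording that ends at recurrence. The number treated is not given, and recruitment was incomplete. The textual gap does not depend on these figures.

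It would go too far to infer that safety data are suppressed. Laboratory results are listed in full, fatal TEAEs are listed and counted, and later deaths should appear in disposition. What is missing is a planned comparison, not the data.

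**What to change.** - **SAP 7.4:** add a table of worst CTCAE grade per patient by actual treatment arm, following protocol 8.6.3, and keep the listing. Restricting the table to post-baseline values would be a sensible clarification, but protocol 8.6.3 does not say it. Align the description of sampling with the scheduled draws (Screening, Day 1, and the Safety Follow-up or Month 3 visit).
- **SAP 7.3.4:** add a sentence committing to a table of every death recorded in the study by treatment actually received, following protocol 8.6.1.2. Cause of death and days from instillation would be an optional addition beyond the protocol.
- **Alternatively:** if either reduction is intended, state it with a reason in the Summary of Changes.

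The cost is a few lines of SAP text and two descriptive tables from data already collected. Both tables may be sparse. No new patients, visits or procedures are needed.

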7.4 Clinical Laboratory Evaluations

Clinical laboratory samples are collected pretreatment and throughout study. Where applicable, all laboratory results will be classified according to the NCI CTCAE version 4.03. Results will be provided in listing.

